8 SAFETY ASSESSMENTS AND PROCEDURES

8.1 SAFETY AND OTHER ASSESSMENTS

Study procedures and evaluations to monitor safety and support the understanding of the study intervention's safety, or that are done for other purposes (e.g., screening, eligibility, enrollment), are listed below. Most assessments should be completed as per standard of care monitoring and data will be extracted from the electronic health records and entered in the EDC.

Study-Specific Procedure

- Assessment of adverse events

Standard of Care Evaluation – Data prescribed in CRF and extracted from electronic health records.

The information contained in this protocol and all other information relevant to this study are confidential and proprietary information of Strata Oncology Inc., except as may be required by federal, state or local laws or regulation, and may not be disclosed to others without prior written permission of Strata.

Page 39 of 56

- Demographics and disease/medical characteristics including:
 - Participant demographics
 - Disease history (date of first diagnosis, treatment history)
 - Biomarker status (biomarker test results)
 - Medical history including documentation of prior and ongoing medical illnesses and conditions, and surgical procedures (those not related to primary diagnosis), previous diseases and concomitant diseases within the last 30 days before screening
 - Previous and concomitant medication
- Complete or abbreviated physical examination including a review of all body systems. Information to be recorded may include height, weight, organ systems, motor or vision assessment.
- Performance Status (ECOG).
- Vital signs should be assessed including blood pressure, heart rate, body temperature, and respiration rate.
- Standard local laboratory assessments, such as hematology, serum chemistry (albumin, alkaline phosphatase, total bilirubin, bicarbonate, BUN, calcium, chloride, creatinine, glucose, LDH, phosphorus, potassium, total protein, AST, ALT, and sodium).
- Urine pregnancy test for females of child-bearing potential.
- Electrocardiograms and Echocardiograms as indicated for the participant per standard of care guidelines.

Please review the study's operations manual for specific instructions.

8.2 ADVERSE EVENTS AND SERIOUS ADVERSE EVENTS

8.2.1 DEFINITION OF ADVERSE EVENTS (AE)

Adverse event means any untoward medical occurrence associated with the use of an intervention in humans, whether or not considered intervention-related (21 CFR 312.32 (a)).

8.2.2 DEFINITION OF SERIOUS ADVERSE EVENTS (SAE)

An AE or suspected adverse drug reaction is considered serious if, in the view of either the investigator or sponsor, it results in any of the following outcomes:

- Death,
- Life-threatening adverse event,
- Inpatient hospitalization or prolongation of existing hospitalization,
- Persistent or significant incapacity or substantial disruption of the ability to conduct normal life functions, or

The information contained in this protocol and all other information relevant to this study are confidential and proprietary information of Strata Oncology Inc., except as may be required by federal, state or local laws or regulation, and may not be disclosed to others without prior written permission of Strata.

Page 40 of 56

- Congenital anomaly/birth defect.

Important medical events that may not result in death, be life-threatening, or require hospitalization may be considered serious when, based upon appropriate medical judgment, they may jeopardize the participant and may require medical or surgical intervention to prevent one of the outcomes listed in this definition. Examples of such medical events include allergic bronchospasm requiring intensive treatment in an emergency room or at home, blood dyscrasias or convulsions that do not result in inpatient hospitalization, or the development of drug dependency or drug abuse.

8.2.3 CLASSIFICATION OF AN ADVERSE EVENT

8.2.3.1 SEVERITY OF EVENT

All AEs will be assessed by the study investigator using the National Cancer Institute (NCI) Common Terminology Criteria for Adverse Events (CTCAE) version 5.0.

8.2.3.2 RELATIONSHIP TO STUDY INTERVENTION

All AEs must have their relationship to study intervention assessed by the investigator who examines and evaluates the participant based on temporal relationship and their clinical judgment. The degree of certainty about causality will be graded using the categories below. In a clinical trial, the study product must always be suspect.

- **Definitely Related** – There is clear evidence to suggest a causal relationship, and other possible contributing factors can be ruled out. The clinical event, including an abnormal laboratory test result, occurs in a plausible time relationship to study intervention administration and cannot be explained by concurrent disease or other drugs or chemicals. The response to withdrawal of the study intervention (dechallenge) should be clinically plausible. The event must be pharmacologically or phenomenologically definitive, with use of a satisfactory rechallenge procedure if necessary.
- **Probably Related** – There is evidence to suggest a causal relationship, and the influence of other factors is unlikely. The clinical event, including an abnormal laboratory test result, occurs within a reasonable time after administration of the study intervention, is unlikely to be attributed to concurrent disease or other drugs or chemicals, and follows a clinically reasonable response on withdrawal (dechallenge). Rechallenge information is not required to fulfill this definition.
- **Possibly Related** – There is some evidence to suggest a causal relationship (e.g., the event occurred within a reasonable time after administration of the trial medication). However, other factors may have contributed to the event (e.g., the participant's clinical condition, other concomitant events). Although an AE may rate only as "possibly related"

The information contained in this protocol and all other information relevant to this study are confidential and proprietary information of Strata Oncology Inc., except as may be required by federal, state or local laws or regulation, and may not be disclosed to others without prior written permission of Strata.

Page 41 of 56

soon after discovery, it can be flagged as requiring more information and later be upgraded to “probably related” or “definitely related”, as appropriate.

- **Unlikely to be Related** – A clinical event, including an abnormal laboratory test result, whose temporal relationship to study intervention administration makes a causal relationship improbable (e.g., the event did not occur within a reasonable time after administration of the study intervention) and in which other drugs or chemicals or underlying disease provides plausible explanations (e.g., the participant's clinical condition, other concomitant treatments).
- **Not Related** – The AE is completely independent of study intervention administration, and/or evidence exists that the event is definitely related to another etiology. There must be an alternative, definitive etiology documented by the study investigator.

8.2.3.3 EXPECTEDNESS

The study physician will be responsible for determining whether an AE is expected or unexpected. An AE will be considered unexpected if the nature, severity, or frequency of the event is not consistent with the risk information described in the package insert for each interventional product.

8.2.4 TIME PERIOD AND FREQUENCY FOR EVENT ASSESSMENT AND FOLLOW-UP

The occurrence of an AE or SAE may come to the attention of study personnel during study visits and interviews of a study participant presenting for medical care, or upon review by a study monitor.

All AEs, including local and systemic reactions not meeting the criteria for SAEs, will be captured on the appropriate CRF. Information to be collected includes event description, time of onset, investigator's assessment of severity, relationship to study product (assessed only by those with the training and authority to make a diagnosis), and time of resolution/stabilization of the event. Regardless of relationship, all AEs occurring while on study must be documented and followed to adequate resolution.

Any medical condition that is present at the time that the participant is screened will be considered as baseline and not reported as an AE. However, if the study participant's condition deteriorates at any time during the study, it will be recorded as an AE.

Changes in the severity of an AE will be documented to allow an assessment of the duration of the event at each level of severity to be performed. AEs characterized as intermittent require documentation of onset and duration of each episode.

The information contained in this protocol and all other information relevant to this study are confidential and proprietary information of Strata Oncology Inc., except as may be required by federal, state or local laws or regulation, and may not be disclosed to others without prior written permission of Strata.

Page 42 of 56

Study site will record all reportable events with start dates occurring any time after informed consent is obtained until 7 (for non-serious AEs) or 30 days (for SAEs) after the last day of study participation. At each study visit, the investigator will inquire about the occurrence of AE/SAEs since the last visit. Events will be followed for outcome information until resolution or stabilization.

8.2.5 ADVERSE EVENT REPORTING

The investigator is responsible for reporting the information to the study sponsor and local regulatory authorities, as required.

8.2.6 SERIOUS ADVERSE EVENT REPORTING

The investigator will immediately report any SAE to the sponsor, whether or not it is considered study intervention related, including those listed in the protocol or package insert. The report must include an assessment of whether there is a reasonable possibility that the study intervention caused the event. Study endpoints that are SAEs (e.g., all-cause mortality) must be reported in accordance with the protocol unless there is evidence suggesting a causal relationship between the study intervention and the event (e.g., death from anaphylaxis). In that case, the investigator must immediately report the event to the sponsor.

All SAEs will be followed until satisfactory resolution or until the investigator deems the event to be chronic or the participant is stable. Other supporting documentation of the event may be requested by the study sponsor and should be provided as soon as possible.

8.2.7 REPORTING EVENTS TO PARTICIPANTS

Section not applicable

8.2.8 EVENTS OF SPECIAL INTEREST

All deaths that occur during the study must be reported as follows:

- Death that is clearly the result of disease progression should be documented but not reported as an SAE.
- Where death is not due (or not clearly due) to progression of the disease under study, the AE causing the death must be reported as an SAE within 24 hours of knowledge of the event.
- Deaths with an unknown cause should always be reported as an SAE.

8.2.9 REPORTING OF PREGNANCY

The information contained in this protocol and all other information relevant to this study are confidential and proprietary information of Strata Oncology Inc., except as may be required by federal, state or local laws or regulation, and may not be disclosed to others without prior written permission of Strata.

Page 43 of 56

Female participants with the ability to get pregnant will be required to be on a double barrier birth control method for the duration of the trial in all cohorts. Male participants with female partners of child-bearing potential should be advised on birth control approach based on the study drug cohort.

Participants who become pregnant during the study period should not receive any additional doses but will not be discontinued from the study to allow for tracking of event outcome.

Participants will be asked the date of their last menstrual period in lieu of a pregnancy test at each visit. Pregnancy in a participant who has received study intervention is required to be reported within 24 hours of knowledge of the event to the sponsor.

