7 STUDY PROCEDURES AND SCHEDULE

7.1 STUDY PROCEDURES

7.1.1 STUDY SPECIFIC PROCEDURES

All procedures listed here are specific to the study and are not part of standard clinical care:

- Review and sign informed consent
- Eligibility criteria review
- Biological specimen collection
 - Two 10 milliliter (mL) tube of blood (20 mL total) will be collected via venipuncture
- Archival FFPE tissue submission (if historical CGP and/or Strata RNA profiling results are unavailable or as otherwise indicated within the cohort-specific criteria)
- Biomarker confirmation (biomarker test results)
- Data collection of any standard of care procedures conducted as part of regular clinical visits
- Study drug dispensing
- Study drug administration
- CT/MRI scan of abdomen, chest, and pelvic area
- Tumor assessments (RECIST 1.1 or iRECIST)
- Drug administration and accountability
- Evaluation and documentation of adverse events (AEs) or serious adverse events (SAEs)
- Electrocardiograms (EKGs) and/or echocardiogram (Echo) are required for eligibility determination at screening. If not done as part of standard of care work-up or historical

The information contained in this protocol and all other information relevant to this study are confidential and proprietary information of Strata Oncology Inc., except as may be required by federal, state or local laws or regulation, and may not be disclosed to others without prior written permission of Strata.

Page 30 of 56

EKG and/or Echo are not available, these tests should be performed as research procedures.

- A serum pregnancy test is required if the pre-treatment urine pregnancy test is positive or inconclusive. Pregnancy tests must be documented as negative within 3 days of study treatment.

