7.1.2 STANDARD OF CARE PROCEDURES

All procedures listed here may be conducted as part of standard clinical care but are not required to be done for study purposes only (refer to **Tables C and D** for the Schedule of Activities). These SOC procedures are not billable to the study and should only be done if needed for clinical care.

Regardless of whether the following are performed during a standard of care clinical visit, or in combination with study procedures, all relevant data collected must be entered into the EDC system. The data entry of both SOC procedures and study-specific procedures is a required study activity to meet study objectives and endpoints.

- Demographics and disease/medical characteristics including:
 - Demographics
 - Disease history (date of first diagnosis, treatment history)
 - Current medical history (within the last 30 days) including medical illnesses and conditions, and surgical procedures not related to primary diagnosis.
 - COVID-19 vaccination and disease history
 - Previous and concomitant medication within the last 30 days before screening
- Complete or abbreviated physical examination
 - Information to be recorded may include results, abnormal findings, and clinical significance for various body systems examined.
- Performance Status (ECOG)
- Vital signs, including height, weight, blood pressure, heart rate, and respiration rate
- Standard local laboratory assessments including hematology, serum chemistry (albumin, alkaline phosphatase, total bilirubin, bicarbonate, blood urea nitrogen (BUN), calcium, chloride, creatinine, glucose, lactate dehydrogenase (LDH), phosphorus, potassium, total protein, aspartate aminotransferase (AST), alanine aminotransferase (ALT), and sodium)
- Urine pregnancy test for females of childbearing potential within 3 days prior to treatment.

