7.2.1 SCHEDULE OF ACTIVITIES

The schedules of activities (SOA) for both the tdMeta and μMeta cohorts are detailed in **Table C** and **Table D**. StrataPATH is designed to mimic real-world practice and will have a limited number of study-specific visits (**Section 7.1**). The visit schedules are comprised of a combination of study-specific visits and standard of care (SOC) visits. Participants will be followed for up to 3 years from the time of consent.

SOC procedures listed in the SOA typically occur during standard clinical visits and are to be documented within the EDC system at the timepoints outlined in the SOA.

The information contained in this protocol and all other information relevant to this study are confidential and proprietary information of Strata Oncology Inc., except as may be required by federal, state or local laws or regulation, and may not be disclosed to others without prior written permission of Strata.

Page 32 of 56

Table C: StrataPATH Schedule of Activities – tdMeta Cohorts

SCHEDULE OF ACTIVITIES STR-004-001: StrataPATH tdMeta Cohorts	STUDY VISITS (participation up to 3 years)			
	Screening	Baseline	On Treatment	Post-Treatment ^g
Study Procedures				
Review and Sign Informed Consent Form	X			
Eligibility Criteria Review (Main and Cohort-Specific)	X	X		
Biomarker Confirmation	X			
CT Scan or MRI of Abdomen, Chest, and Pelvic Area		X ^a	X ^{b,c}	
RECIST 1.1 (or iRECIST) Assessment		X	X ^{b,c}	
Blood Draw: Whole Blood		X	X ^{b,c}	
FFPE Tissue Collection	X ^d			
Study Drug Administration		X ⁱ	X ⁱ	
Study Drug Accountability		X	X	X ^h
Study Drug Discontinuation				X ^h
Standard of Care (SOC) Procedures^e				
Documentation of Biomarker Results	X ^e			
Demographics	X ^e			
Medical History	X ^{e,f}		X ^e	X ^e
Cancer Diagnosis	X ^e			
Prior and Concomitant Medications	X ^{e,f}		X ^e	X ^e
Physical Exam (Complete or Abbreviated)	X ^e		X ^e	X ^e
ECOG Performance Status	X ^e	X ^e	X ^e	X ^e
Height, Weight, Vital Signs	X ^e		X ^e	X ^e
Electrocardiogram (EKG)	X ^j		X ^e	X ^e
Echocardiogram (Echo)	X ^j			
Hematology	X ^e		X ^e	X ^e
Serum Chemistry	X ^e		X ^e	X ^e
Urine Pregnancy Test, Serum Pregnancy Test ^k	X ^e	X ^e	X ^e	
Safety Evaluation				
Adverse Events/Serious Adverse Events		X	X	X

^aIf a scan was performed within 28 days of the baseline visit, these results should be submitted to the study.

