^bCollect every 8 weeks (± 2 weeks) during year 1 on treatment. After year 1 of treatment, collect every 12 weeks (± 2 weeks). Collect upon disease progression.

^cConfirmation of progression (e.g., confirmatory scan 4 weeks after initial progression assessment).

^dOnly required if historical comprehensive genomic or Strata RNA profiling results are not available or otherwise indicated within the cohort-specific criteria. Site should collect and submit a leftover tumor tissue specimen to the Strata Lab for confirmatory testing with a central next generation sequencing test.

^eThe specified SOC procedures should be conducted only if they are necessary for clinical care and should not be done for research purposes only. If any of these SOC activities are conducted at a regular clinic visit, the data obtained must be entered in the EDC for the study.

^fEnter information from medical records obtained up to 30 days prior to the screening visit.

^gEvery 3 months for up to 3 years from the date of consent or until death, whichever comes first.

^hStudy drug will be discontinued upon progression or per physician discretion. Study drug discontinuation and accountability activities will only be performed once during post-treatment.

ⁱThe frequency of study drug dispensing and administration will be determined by the biomarker/study drug cohort in which the patient is enrolled.

^jIf not SOC and historical data not available, can be research activity.

^kOnly if urine test is positive or inconclusive; serum test can be research activity.

The information contained in this protocol and all other information relevant to this study are confidential and proprietary information of Strata Oncology Inc., except as may be required by federal, state or local laws or regulation, and may not be disclosed to others without prior written permission of Strata.

Page 33 of 56

Table D: StrataPATH Schedule of Activities – μMeta Cohorts

SCHEDULE OF ACTIVITIES μMeta Cohorts STR-004-001 - StrataPATH	STUDY VISITS (participation up to 3 years)			
	Screening	Baseline	On Treatment	Post-Treatment ^e
Study Procedures				
Review and Sign Informed Consent Form	X			
Eligibility Criteria Review (Main and Cohort-Specific)	X	X		
Biomarker Confirmation	X			
Blood Draw: Whole Blood		X	X ^b	
FFPE Tissue Collection	X ^a			
Study Drug Administration		X ^g	X ^g	
Study Drug Accountability		X	X	X ^f
Study Drug Discontinuation				X ^f
Standard of Care (SOC) Procedures				

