7.2.2.3 ON TREATMENT

- Review of medications
- Negative pregnancy test (urine or serum)
- Obtain two 10 mL tubes of whole blood every 8 weeks during the first year of treatment and every 12 weeks thereafter and once upon disease progression

The information contained in this protocol and all other information relevant to this study are confidential and proprietary information of Strata Oncology Inc., except as may be required by federal, state or local laws or regulation, and may not be disclosed to others without prior written permission of Strata.

Page 35 of 56

- Complete research blood collection form
- Conduct CT scan or MRI of abdomen, chest, and pelvic area every 8 weeks during the first year of treatment and every 12 weeks thereafter
 - At progression, perform a confirmatory CT scan or MRI (e.g., 4 weeks after initial progression assessment)
- Complete RECIST 1.1 (or iRECIST) assessment every 8 weeks during the first year of treatment and every 12 weeks thereafter
 - At progression, perform RECIST 1.1 (or iRECIST) assessment (e.g., 4 weeks after initial progression assessment)
- Dispense study drug
- Administer study drug and/or review administration instructions with participant
- Perform drug accountability
- Enter data from any standard of care procedures in the EDC, including ECOG status
- Document any AEs or SAEs

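### The protocol gives three incompatible rules for pregnancy testing on treatment: listed without condition, done only if clinically needed, and replaced by a menstrual date

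*Protocol*

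**What the plan says.** **Visit lists.** Protocol 7.2.2.3 (tdMeta, on treatment) includes the bullet "Negative pregnancy test (urine or serum"), and 7.2.3.3 (μMeta, on treatment) carries the same bullet. Neither attaches a condition or a frequency. The baseline lists in 7.2.2.2 and 7.2.3.2 contain it too.

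**Schedule tables.** In Tables C and D (7.2.1) the row "Urine Pregnancy Test, Serum Pregnancy Test" sits under standard-of-care procedures and is marked at screening, baseline and on treatment. Each mark carries footnote e (Table C) or c (Table D), under which the "specified SOC procedures should be conducted only if they are necessary for clinical care". Section 7.1.2 includes the urine test in a list of procedures that "are not required to be done for study purposes only".

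**Study-specific procedures.** Section 7.1.1 says: "Pregnancy tests must be documented as negative within 3 days of study treatment". Exclusion criterion 6 in 5.2 rules out a woman of childbearing potential with a positive urine test in the 72 hours before treatment, and calls for a serum test if the urine result is positive or cannot be confirmed as negative.

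**Pregnancy reporting.** Section 8.2.9 says: "Participants will be asked the date of their last menstrual period in lieu of a pregnancy test at each visit".

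**The concern.** An instruction to ask for a menstrual date in place of a test cannot be carried out together with a visit list that names a negative test. Nor does either match a schedule under which the test depends on clinical need. Nothing in the protocol ranks these places or confines 8.2.9 to particular visits.

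What is at stake is participant safety and uniform conduct. Section 5.3 warns that study medication may harm a fetus. Section 5.4 requires immediate discontinuation of study treatment if a participant becomes pregnant, and 8.2.9 requires a report to the sponsor within 24 hours of knowledge. Both duties begin only once the pregnancy is known, so the rule for finding it matters. The synopsis foresees 25 to 30 sites. Different sites could follow different sections and each point to protocol text in support, while 12.3 counts any noncompliance with the protocol as a deviation.

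**Working it through.** No arithmetic applies: the point depends on no error rate, effect size or sample size. The check is to set the current passages side by side and ask whether one course of action satisfies them all.

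| Place in the protocol | Visit covered | What it says about the test |
|---|---|---|
| 7.2.2.3, 7.2.3.3 | On treatment | Listed; no condition, no frequency |
| Tables C and D, footnotes e and c | Screening, baseline, on treatment | Standard of care, only if clinically necessary |
| 7.1.2 | Before treatment (within 3 days) | Urine test is standard of care, not required for study purposes alone |
| 8.2.9 | Each visit | Menstrual date asked in place of a test |
| 7.2.2.2, 7.2.3.2 | Baseline | Listed; no condition |
| 7.1.1 | Within 3 days of study treatment | Negative result must be documented |
| 5.2, criterion 6 | Within 72 hours before treatment | Positive test excludes; serum test if not confirmed negative |

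**Step 1: on-treatment lists against 8.2.9.** The lists name a test result as an activity, and 8.2.9 substitutes a question for the test. A site that only asks the date has not done the listed test. A site that tests has not followed the substitution. These two cannot both be met.

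**Step 2: on-treatment lists against the table footnotes.** Where clinical care calls for a test, both are satisfied. Where it does not, the list still names the test while the footnote says it should not be done for research alone. They conflict in that second case.

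**Step 3: footnotes against 8.2.9.** The footnote permits a test when care needs one and the tables mark it on treatment; 8.2.9 puts a question in its place at every visit. These too are different rules.

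**Step 4: do footnotes k (Table C) and i (Table D) resolve it?** No. They let the serum test be a research activity, but only after a positive or inconclusive urine test. They do not make the routine urine test mandatory.

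**Step 5: before treatment.** Read literally, the reference in 8.2.9 to each visit takes in baseline, where 7.2.2.2 and 7.2.3.2 list a test. Separately, 7.1.1 makes a documented negative result mandatory, while 7.1.2 and the footnotes leave the urine test to clinical need. The time windows agree: 72 hours ÷ 24 = 3 days.

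**Step 6: is this superseded text?** No. Every passage in the table belongs to the current body of the protocol; none comes from the summary of changes.

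**The case against.** The best defence is that 8.2.9 is a section on reporting, so sites will work from the schedule. That does not remove the problem. The sentence in 8.2.9 says what is done at visits, and the schedule itself is divided between unconditional visit lists and conditional footnotes.

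A second defence is that the cohort appendices or the operations manual, which are not shown, may add a testing rule. They may, and for that reason the point is that sites could differ, not that they will. A rule held elsewhere would still leave the main text contradicting itself.

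Several stronger readings are tempting but go beyond the text:

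- *A test is required at every on-treatment visit.* The bullets in 7.2.2.3 and 7.2.3.3 give no frequency, although neighbouring bullets for blood draws and scans do. Only 8.2.9 speaks of each visit.
- *A site following the footnotes would not test.* The footnotes allow a test when clinical care needs it.
- *Participants would be dosed through unrecognised pregnancies.* Under 8.2.9 the menstrual date is still asked, and 5.3 and 8.2.9 impose contraception. The text supports later detection as a possibility, not as a likely event.
- *Up to 700 participants are affected.* That is the enrolment ceiling for the whole study, including men and women not of childbearing potential.
- *Section 5.2 demands a documented negative test, in a different window from 7.1.1.* Criterion 6 is worded as exclusion on a positive result. The documentation requirement is in 7.1.1, and the two windows are equal.

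**Conclusion.** The contradiction stands. The current protocol contains three on-treatment rules that cannot all be followed, and the same passages also clash over testing before treatment. The consequence the text supports is limited: sites could differ in whether they test, and a pregnancy could be found later than it otherwise would be, delaying the stop of treatment and the report that depend on finding it.

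The size cannot be expressed as a number, because the protocol does not state how many participants will be of childbearing potential. The sample size, error rates and efficacy analyses are untouched. This is an internal inconsistency that should be corrected, with its weight in safety and conduct rather than inference. The conclusion assumes that the sections carry equal authority, since no order of precedence is stated, and that 8.2.9 means what it literally says.

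**What to change.** Reconcile 5.2, 7.1.1, 7.1.2, Tables C and D with their footnotes, 7.2.2.2, 7.2.2.3, 7.2.3.2, 7.2.3.3 and 8.2.9. A single rule should state what is done at baseline, what is done at on-treatment visits, how often, and whether it is a study procedure or standard of care. The other sections should then refer to that rule rather than restate it. The content of the rule is a clinical decision for the sponsor, and none is proposed here.

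The cost is a protocol wording change, with the IRB review that any amendment requires, and a memo to sites. No analysis or sample-size calculation has to be redone.
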